### **Data monitoring.**

Data collection occurs in the form of a series of quantitative assessments and qualitative interviews. The principal investigator ([name]) will work closely to oversee all data management and analysis issues, along with the project statistical ([name]) and the rest of the study team. The study staff will review all data collection forms on an ongoing basis for data completeness and accuracy as well as protocol compliance. Data verification will be performed weekly by a study research assistant who will not be involved in data collection or have any direct contact with study participants. All intervention sessions and exit interviews will be audiotaped (participant consent will be obtained). Intervention fidelity will be assessed by randomly selecting approximately 10% of sessions and assessing adherence to the protocol based on checklists and scales specifically developed for this study. The group facilitator will also participate in weekly supervision with [name], [name] or a study staff psychologist, where audio of sessions will also be reviewed.

### **Project organization.**

A timeline of study procedures is provided in Table 1 and a timeline of study assessments is provided in Table 4. [name], as the principal investigator and overall project director, will oversee all aspects of the project. She will supervise the research assistants at MGH, and oversee the data management and data analyses. Lastly, [name] will serve as a liaison among the other investigators, and together with the co-investigators, will prepare manuscripts and present findings at national conferences.

### **Training of study staff.**

All proposed staff have participated in the NIH required trainings in participation and conduct of studies that involve human subjects, and any future study staff will do so upon hiring. Training for all staff includes (but is not limited to) Human Subjects, Informed Consent, Good Clinical Practice, Quality Management, Confidentiality and Reporting of Adverse Events. If any study staff discovers any untreated condition (e.g., a mental health condition), they will refer participants to appropriate treatment immediately.

## STATISTICAL ANALYSIS PLAN

## Statistical Plan for Analyses

Power: PAR-14-182 states, "...the R34 should ... enhance the probability of reaching more definitive outcomes in a larger trial... by working out the details of the experimental protocols, including the assessment protocol, the...intervention protocol, as well as the comparison intervention protocol and randomization procedures; examining the feasibility of recruiting and retaining participants into the study conditions; ... collection of preliminary data regarding feasibility, acceptability, safety, tolerability, and target outcomes is appropriate. Given the limited sample sizes that can be supported under this...mechanism, proposing the use of a comparison group for conducting fully powered tests of outcomes (i.e., efficacy) or attempting to utilize the highly variable point estimate of an effect size for power calculations would not be appropriate." As stated in the specific aims, we aim to test the feasibility and acceptability of all study procedures as a primary goal; we will not attempt to use our data to estimate an effect size. We are interested in the sensitivity of our selected measures to detect change. Thus, as an exploratory outcome, we propose to examine the intervention effect of resilience and other secondary outcomes. We have conducted power calculations to ensure any lack of effect would be unrelated to power. We also explored current funded R34 studies of similar scope that are currently funded by NCCIH, and our sample size is well within the range of what is documented in these studies (e.g., 5R34AT008423, 1R34AT007935).

Power calculations are based on samples of older, HIV-infected women when available. When data from older HIV-infected women were not available, data from samples of older women, women, or HIV-infected populations were used. We also examined data from community samples. We calculated power estimates for the primary outcome (resilience as measured by the CD-RISC) and for two of the secondary outcomes, depressive symptoms and health related quality of life. With respect to resilience, from Dodding et al., we estimate the standard deviation of change due to the intervention to be 11.8. With 30 patients per group, we will have 80% power to detect a change in resilience of 6.2 points or greater, in absolute value, based on a paired t-test at the 0.05 two-tailed significance level. We estimate the population mean and standard deviation to be approximately 76+/-13 for community-based controls, and 71.7+/-12.5 for a community-based sample of post-menopausal women with sub-clinical depression (N=401). A change of 6.2 points corresponds to approximately 1/2 of a standard deviation for both of these populations (i.e., an effect size of 0.5). Comparing the post-pre differences between treatment arms, we estimate that we will have 80% power to detect an absolute difference of 8.7 on the CD-RISC, based on a two-sample t-test at the 0.05 two-tailed significance level (an effect size of 0.7, which corresponds to a medium-large effect size.

For depressive symptoms, Ickovics et al. reported that 42% of HIV seropositive women were depressed, based on reporting a CES-D score of >16 for 75% of more of study visits. Assuming that the population proportion of participants with elevated depressive symptoms in the placebo arm at the end of the study is 0.42, then with 30 participants per arm, we will have 80% power to detect that the corresponding treatment proportion is <0.12 or >0.76. For health related quality of life, Mrus et al. reported a mean for the overall health domain of HRQoL in women engaged in HIV treatment of 71.4, with a standard deviation of 13.8. Using this standard deviation, with 30 participants per arm, we will have 80% power to detect if the absolute mean between-group difference in this quality of life measure at the end of the study is 10.2 points or greater, based on a two-sample t-test at the 0.05 two-tailed significance level. In summary, we are confident that we can achieve a medium to large effect size across multiple outcomes with the proposed N.

**Analyses:** With respect to quantitative data, we will compare each outcome between groups using mixed- model regression analyses, with subject as a random effect. Fixed covariates will include time in study (baseline, end of treatment, 3 month follow-up) and time since diagnosis. Other covariates, such as education, socioeconomic status, and history of exposure to traumatic events will also be considered. We will consider exploratory mediational and moderational analyses, based on procedures outlined by Hayes. We will assess adherence in the active treatment arm, in particular to determine if adherence is related to change in the primary outcome. We will perform exploratory multivariate analyses among the outcomes, including graphical methods and the calculation and testing of correlations and partial correlations. We will examine patterns in missing data in order to see if missingness is related to measured patient characteristics. We will adjust for missing data using multiple imputation as appropriate. We will adjust for multiple comparisons using the method of Hothorn, Bretz and Westfall. Statistical analyses will be performed using “R” software.

All qualitative data will be analyzed using standard qualitative methodologies described by the Office of Behavioral and Social Sciences Research at the National Institutes of Health. Specifically, data will be analyzed using content analysis, an iterative, multi-step process as described by Miles and Huberman and Strauss and Corbin. The investigators will use NVivo software (version 10) to organize data and to facilitate analyses. Two study team members will independently review the transcripts in order to generate an overarching thematic framework for data interpretation, in which major and minor themes are identified. Using multiple coders also enhances the validity of the analysis. The investigators will compare their thematic frameworks for consistency, and any discrepancies will be discussed until there is agreement on the thematic framework. Data will be reexamined, messages will be extracted and highlighted, and ongoing discussion between coders will allow for further theorizing and making interconnections between research questions, coding categories, and raw data.

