## **1. SPECIFIC AIMS**

**Specific Aims.** This is the second phase of a two-part study. In the first phase (MGH IRB Protocol #2017P000404), we adapted an existing resiliency intervention, the Relaxation Response Resiliency Program (3RP), to the needs of women ages 50 and over who are living with HIV. We conducted preliminary testing of the refined group intervention via an open pilot study (N=13 enrolled) across two sites, MGH and Boston Medical Center), and conducted individual exit interviews to solicit feedback on the intervention, including experiences with the assessment protocol, intervention content, and number and duration of sessions. Data from these interviews were used to make adaptations to the manual in an iterative fashion after each of the three open pilot groups, and the final product will now be tested via a small randomized controlled trial.

Specifically, we will conduct a randomized study (N=up to 60) of the adapted 3RP intervention among groups of women living with HIV, ages 50 and over. Our primary aim is to test the feasibility and acceptability of all study procedures; we hypothesize that our protocol will be both feasible and acceptable. We will also examine data on the effect of the intervention on primary (e.g., resilience) and secondary outcomes of interest, but these analyses are purely exploratory, and we are most interested in how well our selected measures may be sensitive to change. Secondary outcomes will include changes in measures of psychosocial distress (depressive symptoms, anxiety, social support, and quality of life) and HIV / physical health outcomes (suppressed viral load, decreased symptom burden, improved cognitive and physical status). We hypothesize that participants in the treatment condition will experience greater improvements in resilience, psychosocial distress, and HIV / physical health outcomes. Data from this second phase of the study will inform the eventual development of a full-scale randomized controlled trial.

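### The SAP says its power calculations rule out low power as the reason for a null, which its own figures contradict, and it names no summary for its question of whether the measures are sensitive to change

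*Combined protocol and SAP*

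**What the plan says.** The Specific Aims make feasibility and acceptability primary and call the outcome analyses exploratory. Of those analyses the protocol says "we are most interested in how well our selected measures may be sensitive to change".

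The power paragraph of the SAP's Statistical Plan for Analyses first quotes the funder, including that "attempting to utilize the highly variable point estimate of an effect size for power calculations would not be appropriate". It then says "we will not attempt to use our data to estimate an effect size", followed by "We are interested in the sensitivity of our selected measures to detect change". From this it concludes that, "as an exploratory outcome, we propose to examine the intervention effect of resilience and other secondary outcomes". The next sentence is "We have conducted power calculations to ensure any lack of effect would be unrelated to power".

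The power figures for resilience assume 30 per group, a change SD of 11.8 and two-sided 0.05 tests. They give 80% power for a within-group change of 6.2 points (paired t-test) and for a between-arm difference in change of 8.7 points (two-sample t-test). The SAP labels these as effect sizes of 0.5 and 0.7.

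For the analysis itself, "we will compare each outcome between groups using mixed- model regression analyses, with subject as a random effect". On time, "Fixed covariates will include time in study (baseline, end of treatment, 3 month follow-up) and time since diagnosis". No group-by-time term is named, and an adjustment for multiple comparisons is planned. The protocol's Data analytic plan adds descriptive statistics on indicators of change in the psychosocial measures but does not define them. The control arm, described under Study procedures and data collection, is supportive group therapy matched on number and length of sessions.

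**The concern.** There are two linked problems.

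First, the power sentence tells the reader in advance how to take a null result: power is not the explanation. A 30-per-arm comparison cannot support that for moderate effects. It also sits badly with the funder text quoted in the same paragraph, which says that fully powered tests of outcomes are not appropriate here.

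Second, whether a measure responds to change and whether one arm changed more than the other are different questions. The control is active, so both arms may improve, and a measure that records this faithfully can still show no between-arm difference. No responsiveness statistic, interval or per-arm change estimate is specified.

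The pilot is meant to inform a full-scale trial. The risk is that a null is read as evidence of no effect, or that a sound instrument is dropped as insensitive.

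**Working it through.** **Inputs (SAP, power paragraphs):** n = 30 per arm; SD of change 11.8; two-sided alpha 0.05. All powers use the noncentral t distribution, without dropout or multiplicity adjustment, as in the SAP.

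**1. Reproduce the SAP's figures.**
- Within arm, paired test: ncp = (δ/SD)·√n. At δ = 6.2, 6.2/11.8 = 0.525 and power is 79.4%. The change detectable at 80% power is 6.24 points.
- Between arms, two-sample test: ncp = (δ/SD)·√(n/2). At δ = 8.7, 8.7/11.8 = 0.737 and power is 80.2%. The difference detectable at 80% power is 8.68 points.

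Both stated figures reproduce.

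**2. Between-arm power at smaller differences, same inputs.**

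| Difference in change | In SDs of change | Power, 30 per arm |
|---|---|---|
| 8.7 points | 0.74 | 80% |
| 6.2 points | 0.53 | 52% |
| 5.9 points (0.5 × 11.8) | 0.50 | 48% |
| 3.5 points (0.3 × 11.8) | 0.30 | 21% |

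A true between-arm difference of half an SD of change would be missed in about 52% of such trials (100 − 48).

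**3. Fewer analysed (assumption).** The SAP makes no allowance for dropout. In Phase I, 10 of 13 enrolled women took part in the intervention (76.9%). Applied to this trial, 30 × 10/13 ≈ 23 per arm, which gives 38% power at 0.5 SD. The range between 30 and 23 analysed per arm is therefore 48% to 38%.

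**4. Can a between-arm test show responsiveness?** The standardised response mean (SRM) is mean change divided by SD of change. Suppose both arms truly change with SRM 0.5.
- Paired test within one arm, n = 30: power 75%.
- Between-arm test: the true difference is zero, so it rejects 5% of the time, its type I error rate.

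The measure responds in both arms, and the between-arm test has no means of showing it.

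**5. What the alternative summary would deliver.** Exact noncentral-t 95% intervals:
- SRM 0.50, n = 30: 0.12 to 0.88
- SRM 0.50, n = 23 (assumed): 0.06 to 0.93
- between-arm standardised difference 0.50, 30 per arm: −0.02 to 1.01

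**The case against.** **The disclaimer in context.** A reader might infer that the SAP refuses to produce any standardised estimate. The documents do not support that. The sentence directly follows funder text about using a pilot effect size for power calculations, and the natural reading is that narrower one. The SAP itself goes on to speak in effect sizes. What stands is that the sentence does not state its limit.

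**The plan is not purely between-arm.** The power section considers a within-arm paired change, the model includes time at three visits, and the protocol promises descriptive indicators of change. All true. But the paired test appears only in the power section, a time term without a group-by-time interaction does not give per-arm change, and the indicators are undefined.

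**Reporting is not limited to p-values.** A reader might also infer that the trial would end with p-values alone and could not choose measures. Nothing says so. Mixed models give estimates and standard errors, and assessment burden and exit interviews also bear on the choice of measures.

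**The SAP never claims 80% power at 0.5 between arms.** Correct: it attaches 0.5 to the within-arm test and 0.7 to the between-arm test, and both reproduce. The error lies in the general sentence about any lack of effect. Even at the stated differences, 80% power leaves a 20% miss rate.

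**SRM is one index among several and does not settle the question.** Also fair. Without an external anchor, a low SRM cannot by itself separate an insensitive measure from no true change, and the intervals are wide. That is a reason to report the uncertainty and label the result exploratory.

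**Conclusion.** The power sentence is wrong as written. On the SAP's inputs, low power remains a live explanation for a between-arm null at any difference much below 0.74 SD of change: power is 52% at 6.2 points, 48% at 0.5 SD and 21% at 0.3 SD. With 23 analysed per arm it is 38% at 0.5 SD, an assumption taken from Phase I participation, before make-up and call-in sessions were added. Multiplicity adjustment would lower these figures further; I have not quantified that.

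The sensitivity-to-change question is underspecified rather than ruled out. Its only specified inferential route is a between-group comparison with an active control, which does not measure responsiveness. The effect-size disclaimer needs its scope stated.

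The powers depend on the standardised difference, so they hold whatever scale the 11.8 comes from. The point equivalents hold only if 11.8 applies to the instrument in use. Because these outcomes are exploratory in a feasibility pilot, the point concerns interpretation and reporting and does not undermine the primary aim.

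**What to change.** In the SAP's Statistical Plan for Analyses:

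1. Delete the sentence saying that power calculations ensure a lack of effect is unrelated to power. State instead that a non-significant between-arm difference will not be read as no effect or as an insensitive measure.
2. Limit the disclaimer: the data will not be used to estimate an effect size for powering the next trial.
3. Define the indicators of change. For each instrument and each follow-up visit at which it is collected, report per-arm mean change, SD of change and SRM, plus the between-arm standardised difference in change, each with a 95% confidence interval and labelled exploratory. Naming a group-by-time term would let the mixed model supply the per-arm changes and their contrast.
4. Add a caution that the intervals will be wide, and that without an external anchor a low SRM does not by itself show an insensitive measure.

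The cost is a few sentences of SAP text, the same definition in the protocol's Data analytic plan, and a few lines of analysis code on data already planned. No change to sample size, visits or participant burden is needed.

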#### Resilience.

*Resilience:* The Connor-Davidson Resilience Scale (CD-RISC) is a self-report measure of resiliency comprised of 10 items rated on a five-point scale (0 = not true at all, 1 = rarely true, 2 = sometimes true, 3 = often true, 4 = true nearly all the time). Items capture various aspects of resilience including adaptability to change, availability and use of social support, and problem-solving style. Total scores range from 0-40; high scores indicate greater resilience. The CD-RISC has demonstrated good psychometric properties in previous research, including among medical populations.

*Measure of Current Status (MOCS-A):* The MOCS-A is a 13-item self-report measure of stress reactivity and coping, which will be administered at baseline and post treatment. It was developed to assess one's current self-perceived status on several skills targeted by the intervention, including the ability to relax at will, recognize stress-inducing situations, restructure maladaptive thoughts, be assertive about their needs, and choose appropriate coping responses. Statements are rated from 0 (I cannot do this at all) to 4 (I can do this extremely well). Scores range from 0-52; higher scores suggest better coping skills.

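### The SAP's power calculations do not rule out low power as the reason for a non-significant between-arm result: its own t-test gives 80% power at 8.7 CD-RISC points but about 52% at 6.2

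*Combined protocol and SAP*

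**What the plan says.** The Power paragraphs of the SAP (Statistical Plan for Analyses) make feasibility and acceptability the primary goal. They cite the funder's notice that fully powered efficacy tests do not suit this type of grant, and commit to not deriving an effect size from the data. They then state: "We have conducted power calculations to ensure any lack of effect would be unrelated to power". The sentence sets no minimum effect size.

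The calculations that follow are:

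- **Resilience, within arm:** "80% power to detect a change in resilience of 6.2 points or greater, in absolute value, based on a paired t-test", with an SD of change of 11.8 and 30 women per group. The SAP adds: "A change of 6.2 points corresponds to approximately 1/2 of a standard deviation for both of these populations", and labels this an effect size of 0.5. The population SDs it cites are 13 and 12.5.
- **Resilience, between arms:** "80% power to detect an absolute difference of 8.7 on the CD-RISC", by two-sample t-test on the post-minus-pre differences. The SAP labels this 0.7, medium to large.
- **Depression:** with 42% elevated in the control arm, "80% power to detect that the corresponding treatment proportion is <0.12 or >0.76". No test is named.
- **Quality of life:** with an SD of 13.8, 80% power if the "between-group difference in this quality of life measure at the end of the study is 10.2 points or greater".

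The section concludes that the sample size supports medium to large effects across several outcomes. The Analyses paragraph plans to compare outcomes between groups by mixed model and to adjust for multiple comparisons.

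**The concern.** For an absence of effect to be unrelated to power, power would have to be high at every effect size a reader might care about. The only 80% figure tied to an effect of 0.5 concerns change within one arm, which is not a treatment effect. The between-arm targets are all larger.

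What is at stake is how a non-significant comparison is interpreted. Protocol section 1 says the outcome analyses ask how sensitive the measures are to change, and that the data will inform a full-scale trial. If power is declared ruled out in advance, a non-significant difference points to an insensitive measure or an ineffective programme, when small numbers may be the explanation.

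**Working it through.** **Inputs (SAP, Power):** SD of change 11.8; n = 30 per arm; two-sided 0.05; population SDs 12.5 and 13; quality-of-life SD 13.8; depression proportions 0.42 against 0.12 or 0.76. Power for the t-tests comes from the noncentral t distribution.

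**1. Reproduce the SAP's t-test figures.**

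- Paired, within arm: noncentrality = 6.2 / (11.8/√30) = 6.2 / 2.154 = 2.88, df 29. Power 79.4%. Agrees with the stated 80%.
- Two-sample, between arms: standard error = 11.8 × √(2/30) = 3.047. Noncentrality at 8.7 = 8.7 / 3.047 = 2.86, df 58. Power 80.2%. Agrees.
- Quality of life: standard error = 13.8 × √(2/30) = 3.563. Noncentrality = 10.2 / 3.563 = 2.86. Power 80.4%. Agrees.

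**2. Use the same two-sample test at smaller differences.**

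| Between-arm difference | Meaning | Noncentrality | Power |
|---|---|---|---|
| 8.7 | SAP target | 2.86 | 80% |
| 6.5 | half of SD 13 | 2.13 | 55% |
| 6.25 | half of SD 12.5 | 2.05 | 52% |
| 6.2 | SAP's within-arm figure | 2.03 | 52% |
| 5.9 | half the SD of change | 1.94 | 48% |

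**3. Size of the targets.** 8.7/11.8 = 0.74 SD of change; 8.7/13 = 0.67 and 8.7/12.5 = 0.70 of the population SDs. Quality of life: 10.2/13.8 = 0.74 SD.

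**4. Depression.** Exact enumeration of all outcomes with 30 per arm gives, for 0.42 against 0.12, 77% by uncorrected chi-square and 68% by Fisher's exact test. For 0.42 against 0.76 it gives 78% and 69%.

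**5. Precision.** The 95% half-width for a two-sample t-test on change is 2.002 × √(2/30) = 0.52 SD of change, or 0.517 × 11.8 = 6.1 points. An estimate below about 6.1 points is therefore non-significant. Any estimate above 6.2 − 6.1 = 0.1 points in favour of the programme leaves 6.2 inside the interval. Any estimate between 8.7 − 6.1 = 2.6 and 6.1 points is non-significant and leaves even 8.7 inside it.

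**6. Planned mixed model (illustration only).** The SAP names neither the contrast nor baseline adjustment. I assume complete data, a sustained effect, and r = 1 − 11.8²/(2 × SD²), which is 0.55 for SD 12.5 and 0.59 for SD 13. These SDs come from different samples. Power at 6.2 points:

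- Baseline-adjusted, one post visit: residual SD = SD × √(1 − r²) = 10.40 or 10.51; power 61–62%.
- Baseline-adjusted, mean of two post visits, all visits equally correlated: residual SD = SD × √((1 + r)/2 − r²) = 8.57 or 8.70; power 77–79%.

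**7. Loss to follow-up (assumed).** With 27 analysed per arm, t-test power is 76% at 8.7 points and 47% at 6.2. With 23 per arm (30 × 10/13, the Phase I participation rate), it is 69% and 41%.

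**The case against.** The strongest reply has three parts. First, the SAP ties 6.2 points to a paired test and separately gives 8.7 points for the between-arm comparison, so a careful reader can see which effect has 80% power. Second, the analyses are declared exploratory, and no stopping rule, go/no-go rule or sample size depends on the sentence. Third, the planned analysis is a mixed model, so 52% is not its power. All three stand, and they limit the consequence. They do not make an unqualified sentence true, and no other part of the plan qualifies it.

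Four stronger readings are tempting and are not supported:

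- *The SAP's power arithmetic is wrong.* The t-test figures reproduce. Only the depression figure falls short: a few points by chi-square, more by Fisher's test.
- *6.2 points, or half an SD, is the between-arm target.* No section names a smallest difference that matters. It serves here as an example because the SAP itself labels it 0.5.
- *A null result could never argue against a half-SD effect.* An estimate of exactly zero would have an interval of ±6.1 points, which excludes 6.2 to 6.5 points, though not half the SD of change (5.9). The difficulty is with non-significant estimates above zero.
- *The trial needs more women.* The primary aim is feasibility and acceptability, and the SAP disclaims fully powered efficacy tests.

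**Conclusion.** The sentence claims a property the design has not been shown to have. By the SAP's own two-sample t-test, 80% between-arm power is reached only at about 0.74 SD, for both resilience (SD of change) and quality of life (SD of the end-of-study score). Power is about 52% at 6.2 points and about 48% at half the SD of change. The depression claim is nearer 77% or 68% than 80%, depending on a test the SAP does not name.

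These figures assume 30 analysed per arm, the same SD in both arms, and no allowance for clustering by therapy group or for the planned multiplicity adjustment. Multiplicity adjustment, loss to follow-up and any positive clustering would lower power; the repeated-measures model may raise it. The SAP quantifies none of these. The point is worth correcting, but its reach is confined to the interpretation of exploratory between-arm comparisons.

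A separate matter is that the SAP's resilience inputs ("We estimate the population mean and standard deviation to be approximately 76+/-13 for community-based controls"; and 71.7 in the second sample) cannot arise on the scale described in protocol section 3: "Total scores range from 0-40; high scores indicate greater resilience". Power stated in SD units does not depend on resolving that mismatch.

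**What to change.** 1. **SAP, Power, first paragraph.** Delete the sentence and write:

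   > By two-sample t-test, the exploratory between-arm comparisons of continuous outcomes have about 80% power only for differences of about 0.74 SD. A non-significant result will be reported with the 95% CI from the planned model and treated as inconclusive for effects inside that interval. The CI shows imprecision; its estimate will not serve as the effect size for powering a later trial.

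   Bring the SAP's commitment not to derive an effect size from these data into line with this. If a half-width is quoted, say that it is about 0.52 SD of change for a two-sample t-test on change with 30 analysed per arm.

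2. **SAP, Power, resilience paragraph.** Label the 6.2-point figure as within-arm change only.

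3. **SAP, Power, closing summary.** Replace it with:

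   > With 30 analysed per arm and unadjusted two-sided 0.05, between-arm t-test power is about 80% for 0.74 SD (SD of change for the CD-RISC, SD of the end-of-study score for quality of life) and about 48% for 0.5 SD. It falls with loss to follow-up and multiplicity adjustment and may be higher under the repeated-measures model.

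4. **SAP, Power, depression.** Name the test and restate power for 0.42 against 0.12 as about 77% (chi-square) or 68% (Fisher).

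The cost is wording in the SAP and confidence intervals in the exploratory tables. The stated power becomes less favourable. No additional women or data collection are required.
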